examine cognitive function under a variable duration of LFS. We hypothesize that there will be a trend towards improvement in task performance under the LFS setting, measured through reaction time and error rates, and that this improvement will be stable or enhanced with sustained LFS. We hope to utilize these results to inform the design of a larger phase 2 efficacy study. Our specific aims are as follows:

- 1) To monitor the safety of LFS in the STN of patients with PD by examining the psychological, cognitive, and motor consequences of LFS
- 2) To determine the feasibility of utilizing low frequency DBS to improve cognition in patients with PD by examining if there is a trend toward improved executive function with LFS over high frequency stimulation (HFS) and no stimulation settings.
- 3) To further examine feasibility by determining if the differential effects of LFS versus HFS of the STN are long lasting in a small patient group.

At present, DBS stimulators are set at varying stimulation frequencies based on the acute effects of DBS on motor performance, with limited understanding of cognitive consequences. Understanding the effects of different stimulation frequencies on non- motor tasks will help elucidate the mechanism behind cognitive impairment in PD. If our hypotheses are correct it could lead to the development of new treatment plans that involve alternating between low and high frequency stimulator settings to optimize both motor and cognitive domains. Ultimately, focused treatment for cognition may slow the progression from mild cognitive impairment to dementia, improving real world functioning and quality of life.

5) Background

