- (1) Adult men and woman with a diagnosis of PD.
- (2) Patients who are candidates for bilateral STN DBS placement surgery and who will receive this treatment as part of their routine care.
- (3) Willingness to undergo temporary changes in STN DBS generator settings.

PROTOCOL TITLE: Safety and feasibility of using low frequency deep brain stimulation of the subthalamic nucleus to improve cognitive performance in patients with Parkinson's disease

(4) Patients who have a caregiver who is willing to answer psychological screening questions on behalf of the patient.

Exclusion criteria:

- (1) Patients less than 18 years of age.
- (2) Patients who are not candidates for bilateral STN DBS placement surgery.
- (3) Adults unable to consent
- (4) Pregnant woman
- (5) Prisoners
- (6) Patients who score over 20 on the BDI indicating moderate depression

7) Number of Subjects

The target sample size is 22 subjects. The study design is a phase 1 safety and feasibility study. While results may show a trend towards efficacy, we will not be able to power the study toward efficacy. Two of these subjects will be used to evaluate the ease of use of the computerized cognitive test, but will not participate in any other study procedures and data will not become part of the study record. All subjects are to be enrolled locally at UC Davis medical center.

8) Recruitment Methods

a) Study-Wide:

NA

b) Local:

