a) Neuropsychiatric tests. We will perform the BDI and NPI at baseline, at the first experimental session, once by telephone call after 24 hours of LFS, and a fourth time at the final experimental session. The score of the BDI will be compared across sessions and a score that rises above 20 will be considered positive for the development of moderate depression. The NPI assesses frequency, change in severity, and caregiver distress over 12 neuropsychiatric domains and we will look for caregiver reports of significant change across these domains.

b) Motor tests. The Unified Parkinson's Disease Rating Scale (UPDRS) will be performed prior to patient's surgery as part of the patient's routine care. We will repeat the scale at the final experimental session to assess changes in motor symptoms after sustained LFS.

c) Changes in cognitive function will also be assessed as described below.

2. Feasibility. Improvement in cognitive function will be measured by three cognitive tests: the Stroop test, the N-Back test, and the verbal fluency test. We will measure reaction time and error rates and look for significant changes across stimulator frequencies. The results from 20 patients will help us determine if a large-scale study of effectiveness is warranted and feasible.

Describe any primary or secondary safety endpoints.

See above.

PROTOCOL TITLE: Safety and feasibility of using low frequency deep brain stimulation of the subthalamic nucleus to improve cognitive performance in patients with Parkinson's disease

12) Procedures Involved

a) Describe and explain the study design.

The study design is a safety and feasibility study. We aim to identify 20 PD patients who will receive bilateral STN DBS as part of their standard care. We plan to measure the safety of LFS in the STN as measured through psychological, cognitive, and motor scales, and compare cognitive performance with low and high frequency STN DBS. We propose that LFS in the theta range will not negatively affect psychiatric symptoms or alter motor symptoms, and will improve performance on tests of executive functioning.

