We will also examine changes in psychological symptoms. For each individual patient, we will measure the BDI and NPI at baseline, at the first experimental session, by phone call after 24 h LFS, and at the final experimental session. For the BDI, we will consider any score greater or equal to 20 as evidence of moderate depression and will terminate the study for any individual that shows evidence of depression. At the group level, we will calculate

PROTOCOL TITLE: Safety and feasibility of using low frequency deep brain stimulation of the subthalamic nucleus to improve cognitive performance in patients with Parkinson's disease

the percentage of people that develop depression. For the NPI, we will calculate the total score. At the individual level we will look for the development of new symptoms in the 12 subsections. At the group level we will perform an ANOVA to look for significant changes across the 3 time points.

Cognitive Data Analysis:

The cognitive data analysis will examine the effect of theta frequency stimulation on cognitive task performance. Analyses for the Stroop task will include the examination of response time and error rates across stimulator settings. Two (trial type: congruent vs incongruent) by three (Setting: low, high, no stimulation) ANOVAs will be performed for both reaction time and accuracy. Post conflict and post error reaction time adjustments will also be examined across stimulator settings. For the N-back test, ANOVAs will also be performed to assess the effects of complexity (1,2-back) and stimulation frequency (none, high, low) on error rates. For the verbal fluency test, the average number of words generated across stimulation conditions and the change in word number on low and high frequency stimulation settings will be compared. Analyses will be performed using MATLAB and STATA.

Describe any procedures that will be used for quality control of collected data.

a.) Study-Wide:

NA

b.) Local

Describe the local procedures for maintenance of confidentiality.

This research is partly funded by a donation from the Chevo Foundation. The Chevo Foundation will not have access to any of the study documents including the data.

Data files to be stored include group assignment, background information, any head scans if performed, and results from neurocognitive and motor tests.

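### Feasibility is judged by statistical significance across six cognitive outcomes with no primary contrast, estimate or interval, in a study that disclaims efficacy power

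*Combined protocol and SAP*

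**What the plan says.** The protocol describes the purpose of the cognitive data in three ways.

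- **Section 4 (Objectives)** looks for a trend. The hypothesis is "We hypothesize that there will be a trend towards improvement in task performance under the LFS setting, measured through reaction time and error rates", and Aim 2 is to be met by "examining if there is a trend toward improved executive function with LFS over high frequency stimulation (HFS) and no stimulation settings". Trend is not defined.
- **Section 7 (Number of Subjects)** says: "While results may show a trend towards efficacy, we will not be able to power the study toward efficacy". Section 14 repeats this.
- **Section 11 (Study Endpoints)** measures feasibility with the Stroop, N-back and verbal fluency tests: "We will measure reaction time and error rates and look for significant changes across stimulator frequencies". It adds: "The results from 20 patients will help us determine if a large-scale study of effectiveness is warranted and feasible".

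Section 14 (Cognitive Data Analysis) gives the methods. Stroop reaction time and Stroop accuracy each get an ANOVA of trial type by setting (low, high, none). For the same task, "Post conflict and post error reaction time adjustments will also be examined across stimulator settings". N-back error rates get an ANOVA of complexity by frequency. For fluency, mean word counts and the changes under low and high frequency are to be compared, with no method named. No section names a primary cognitive outcome or contrast, a significance level, a multiplicity rule, a confidence interval or a threshold for proceeding to phase 2.

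**The concern.** The study is meant to help decide whether a larger trial is worth running and to inform its design. Both uses need the size of the LFS-versus-HFS difference and its uncertainty. The plan instead searches for significance in a sample that it says is too small for efficacy testing, over outcomes that it does not rank. Whichever result turns out significant could then be presented as the trend. If none does, the plan gives no other reading of the data.

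A second difficulty is that the planned ANOVA effect does not isolate the comparison of interest. Setting has three levels, so a significant effect need not mean that LFS and HFS differ.

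**Working it through.** **Inputs from the documents**
- Section 7: "The target sample size is 22 subjects". Two of these only try out the computer task, so 22 − 2 = 20 are analysed. The documents give no derivation of this number, so there is no calculation to reproduce.
- Section 12: each patient is tested under no stimulation, HFS and LFS, so the comparisons are within patient.

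**Assumptions (not in the documents)**
- Two-sided 0.05 per test.
- Effects expressed as dz, the mean within-patient difference divided by its SD.
- Correlation between tests of 0 to 0.7.

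**1. Count of stimulation-related tests in section 14**

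| Outcome | Tests |
|---|---|
| Stroop reaction time: setting; setting × trial type | 2 |
| Stroop accuracy: setting; setting × trial type | 2 |
| Post-conflict adjustment | 1 |
| Post-error adjustment | 1 |
| N-back errors: frequency; frequency × complexity | 2 |
| Fluency: mean words; change under low and high | 2 |
| **Total** | **10, on 6 outcomes** |

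Counting only the three named ANOVAs, each with its main effect and interaction, also gives 3 × 2 = 6. The narrowest count, the three setting main effects alone, gives 3.

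**2. Chance of at least one false positive if stimulation does nothing**

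For k independent tests this is 1 − 0.95^k:
- k = 3: 14.3%
- k = 6: 26.5%
- k = 10: 40.1%

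The tests share patients, and several share a task, so they are correlated. Simulation with n = 20 and 20,000 runs gives:

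| Correlation | 6 tests | 10 tests |
|---|---|---|
| 0.3 | 24% | 36% |
| 0.5 | 21% | 29% |
| 0.7 | 17% | 22% |

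Counting only false results that favour LFS, the independent figure is 1 − 0.975^k: 14% for k = 6 and about 22% for k = 10. It is lower with correlation.

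**3. Power of one pre-named paired comparison, n = 20**

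Power = P(|T| > 2.093), where T is noncentral t with 19 degrees of freedom and noncentrality dz × √20.
- dz = 0.3: noncentrality 1.34, power 25%
- dz = 0.46: power 50%
- dz = 0.5: noncentrality 2.24, power 57%
- dz = 0.66: noncentrality 2.95, power 80%

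A three-level repeated-measures F-test gives similar results: 25% at dz = 0.3 and 60% at dz = 0.5.

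**4. The two calculations belong to different rules**

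Step 2 applies if any significant test counts. Step 3 applies if one named test counts. Under the any-test rule, and at the same correlations (0 to 0.7), an effect of dz = 0.5 shared by all six outcomes produces at least one significant result 84-99% of the time. If the effect is confined to one of the six, the figure is about 64-66%.

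**5. Precision**

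The half-width of the 95% CI is 2.093 / √20 = 0.47 SD of the within-patient difference.

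**6. What the setting effect tests**

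Under section 12, the first experimental session opens with testing without stimulation. Only the order of the two frequencies is randomised afterwards. A gain from practice between the first and later runs would separate no stimulation from both frequencies and could make the setting effect significant with LFS − HFS = 0. The LFS-minus-HFS contrast compares the two conditions whose order is randomised, so it avoids this.

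**The case against.** The strongest reply is that this is a phase 1 study whose first aim is safety. It discloses that it is not powered for efficacy, and it says only that the results will help and inform a later decision. That is fair, and it rules out several stronger readings.

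- A reader might infer that one significant result among the six to ten triggers phase 2. No such rule is written. What can be criticised is that no rule is written at all.
- A reader might infer that a false positive is likely. Under the stated assumptions it is about 17-40% for six to ten tests: well above 5%, but below even odds.
- A reader might infer that a real effect is likely to be missed. For a single test that holds only below about 0.46 SD, and the documents give no effect size. For a broad effect under an any-test reading it is often untrue.
- A reader might infer that section 14 contains only ANOVAs. It does not. The fluency comparison of changes under low and high frequency comes close to the contrast wanted here, though it has no interval. The post-conflict and post-error analyses name no test.
- A reader might infer that fluency is the obvious primary outcome, since the 12-patient low-frequency STN study cited in section 5 concerns it. The hypothesis in section 4, however, is framed on reaction time and error rates, so the documents do not settle the choice.

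It can also be said that the interval will be wide: an observed 0.3 SD would give 0.3 ± 0.47, or about −0.17 to 0.77. That is true, but it shows the uncertainty that a p-value alone would hide. None of these replies removes the mismatch between a search for significance and the study's stated purpose.

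**Conclusion.** The point holds in a limited form. Section 11 uses significance as the feasibility measure, section 14 applies it to six unranked outcomes, and no primary contrast, estimate or interval is planned. This sits poorly with the power disclaimer and with the undefined trend in section 4. If any significant result were taken as support, the false-positive chance would be about 26-40% with independent tests and about 17-36% at correlations of 0.3-0.7. If one named test were used, 80% power would need about 0.66 SD. Both figures rest on an assumed two-sided 0.05 per test and n = 20 without dropout; at n = 18 the detectable difference is about 0.70 SD. The three-level setting effect adds a separate problem of interpretation that does not depend on these assumptions. This is a cheap improvement: it affects how useful the cognitive results are for phase 2, and it does not touch the safety aim.

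**What to change.** In sections 11 and 14, replace the search for significance with an estimate of the within-patient LFS-minus-HFS difference and its 95% CI for each cognitive outcome. Take it from the first experimental session, where both frequencies are tested. The sponsor should name one outcome as primary before seeing data; whether that is a Stroop measure, an N-back measure or fluency is the sponsor's choice. Its estimate and interval should inform the phase 2 decision and sample size. Label the other outcomes, and the comparisons with no stimulation, exploratory.

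With a single primary contrast no multiplicity adjustment is needed. Keeping every test with a Bonferroni correction instead (0.05/6 = 0.0083 or 0.05/10 = 0.005) would raise the 80%-power difference to about 0.86 or 0.91 SD.

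The cost is two or three sentences and no new data. The downside is that other outcomes can no longer carry the headline, and the no-stimulation part of Aim 2 becomes exploratory.

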to rely on connections between the basal ganglia and the prefrontal cortex (Dadgar et al 2013, Jaywant et al 2014). Furthermore, DBS has been shown in some studies to impair phonemic verbal fluency, which may or may not recover over time (Ehlen et al 2014, Wojtecki et al 2006, Wu et al 2014). These specific letters were chosen based on the frequency of English language words that begin with the letters (Borkowski et al 1967.)

Total testing time will be approximately 30 minutes per stimulation condition with 20 minutes between conditions, resulting in a total time of approximately 30 minutes for the baseline cognitive testing, 2 hours for the first experimental session and 30 minutes for the second experimental session. Additional time will be needed for setup and explanation of the task directions. Finally, 20 minutes of psychological screening will be performed at the baseline session, over the phone between experimental sessions 1 and 2, and following cognitive testing during experimental session 2.

Baseline Testing: 30 min cognitive testing, 20 minute psychological screening (Total Time: approximately 50 min)

Experimental Session 1: 20 minutes psychological screening, 2 hours cognitive testing (Total Time: approximately 2h 20 min)

Phone call between experimental session 1 and 2: 20 minutes psychological screening

Experimental Session 2: 30 min cognitive testing, 20 minute psychological screening, 20 min motor screening (Total Time: approximately 70 minutes)

b) Humanitarian Use Device (HUD)

NA

13) Data and Specimen Banking

No data or specimens will be retained longer than required by law or hospital policy.

14) Data Management and Confidentiality

The target sample size is 22 subjects. The study design is a safety and feasibility phase 1 study. While results may show a trend towards efficacy, we will not be able to power the study toward efficacy.

Safety Data Analysis:

To examine possible effects on motor symptoms, we will screen for changes in the motor section of the UPDRS score after sustained LFS. After each patient is tested, we will calculate individual changes in UPDRS scoring. After the entire patient population is tested, we will use T-tests to determine if there is a significant change in the overall rating scale.

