Safety Data Analysis: To examine possible effects on motor symptoms, we will screen for significant changes in the motor section of the UPDRS score after sustained LFS. After each patient is tested, we will calculate individual changes in UPDRS scoring. After the entire patient population is tested, we will use a T-test to determine if there is a significant change the motor section.

We will also examine changes in psychological symptoms using the BDI and NPI. We will examine percentage of people who convert to moderate depression as indicated by a BDI score 20 or higher. We will also look for significant changes in the BDI and NPI across time using ANOVAs.

Changes in cognition will also be analyzed by looking at reaction time and error rates on different cognitive tests as described previously.

- Any conditions that trigger an immediate suspension of the research.

None.

16) Withdrawal of Subjects

Describe anticipated circumstances under which subjects will be withdrawn from the research without their consent.

Patients unable to perform cognitive tests due to effort or altered mental status.

Patients who experience any change in psychological symptoms that is concerning to the patient, caregiver, or test administrator as assessed through psychological screening tools.

Describe any procedures for orderly termination.

The patient is not undergoing any additional procedures, except for stimulation and cognitive testing.

Describe procedures that will be followed when subjects withdraw from the research, including partial withdrawal from procedures with continued data collection.

Patients' data will be recorded, unless specifically asked to be withdrawn

Patients will continue to be followed for medical management

17) Risks to Subjects

Physical Risk:

- There is minimal to no physical risk. Once the patient's stimulation is turned off, the patient's pre-stimulation symptoms will likely return (Temperli et al 2003).
- There is a small chance that changes in affective symptoms including dysphoria, depression, mania, or psychosis may occur (Smeding et al 2006, Strutt et al 2012). Patients will be carefully screened using standardized assessment tools.
- All cognitive and memory tests are designed to be minimally difficult and pose minimal

PROTOCOL TITLE: Safety and feasibility of using low frequency deep brain stimulation of the subthalamic nucleus to improve cognitive performance in patients with Parkinson's disease

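### The safety hypothesis is absence of harm, but the group-level safety analyses are tests for significant change, with no interval, tolerable limit or stated reading of a null result

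*Combined protocol and SAP*

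**What the plan says.** Safety is the first aim (section 4) and the first endpoint listed (section 11). The hypothesis in section 12(a) is one of absence, namely that LFS "will not negatively affect psychiatric symptoms or alter motor symptoms".

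The group-level analyses are these:
- **UPDRS.** Section 14 (Safety Data Analysis): "we will use T-tests to determine if there is a significant change in the overall rating scale". Section 15 (Safety Data Analysis) refers to the motor part: "we will use a T-test to determine if there is a significant change the motor section".
- **NPI and BDI.** Section 14 plans an ANOVA on the NPI total. Section 15 covers both scales: "We will also look for significant changes in the BDI and NPI across time using ANOVAs".
- **Depression.** Sections 14 and 15 plan the percentage of patients who reach the BDI threshold, without an interval.

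Other safety elements are not significance tests. Each patient's UPDRS change is calculated, new NPI symptoms are looked for patient by patient, and individuals can be halted on BDI, motor or psychological grounds. A committee reviews the data after 4, 8, 12 and 20 patients. No group-level numeric limit is attached to any of these, and the section 15 item on conditions for immediate suspension is answered in the negative.

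On size, section 12(a) states "We aim to identify 20 PD patients who will receive bilateral STN DBS as part of their standard care". Section 7 gives 22 in total, two of whom only try out the computer test. The one statement about power concerns efficacy: "While results may show a trend towards efficacy, we will not be able to power the study toward efficacy". Nothing is said about power or precision for safety.

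**The concern.** A test of no change can give evidence that something changed. When it fails to reject, it gives no evidence that nothing changed. The plan pairs a hypothesis of no harm with tests of that kind and does not say what a non-significant result will mean. Nor does it plan the quantity that would answer the safety question, namely how much worsening the data still allow.

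For the group tests, fewer patients or noisier ratings make a non-significant result more likely when there is real worsening. The results are meant to inform a larger phase 2 study, whose planners need to know what worsening has been excluded; p-values alone will not tell them.

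**Working it through.** The plan states no safety power, alpha, sidedness, SD or margin, so there is no figure of its own to reproduce.

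**Inputs from the protocol.** n = 22 − 2 = 20 (sections 7 and 12(a)). One UPDRS change per patient, from before surgery to the final session (sections 11 and 15).

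**Assumptions.** Two-sided alpha 0.05, a paired t-test, and 20 complete pairs. Changes are in units of the SD of change, because the documents give no SD.

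**Precision of the mean change.** Half-width = t(0.975, 19)/√20 = 2.093/4.472 = 0.47 SD. If the observed worsening falls just short of significance, the upper limit is about 2 × 0.468 = 0.94 SD.

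**Power of the UPDRS t-test** (noncentral t, 19 df, noncentrality d√20):

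| True worsening d (SD of change) | Power | Missed |
|---|---|---|
| 0.3 | 0.25 | 75% |
| 0.4 | 0.40 | 60% |
| 0.5 | 0.56 | 44% |
| 0.6 | 0.72 | 28% |
| 0.66 | 0.80 | 20% |

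**In scale points**, over a range of assumed SDs of change:

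| Assumed SD of change | 95% half-width | Change detectable with 80% power |
|---|---|---|
| 4 | 1.9 | 2.6 |
| 6 | 2.8 | 4.0 |
| 8 | 3.7 | 5.3 |
| 10 | 4.7 | 6.6 |
| 12 | 5.6 | 7.9 |

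**With 16 complete pairs**, the half-width is 0.53 SD, 80% power needs 0.75 SD, and power at 0.5 SD falls to about 0.46.

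**BDI conversion.** With 0 of 20, the exact two-sided 95% upper limit is 1 − 0.025^(1/20) = 16.8%. With 1 of 20 it is 24.9%. A true rate of 10% gives 0 of 20 with probability 0.9^20 = 12%.

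**A margin-based conclusion.** If the true change is zero, 20 patients give 80% power to exclude a worsening of about 0.66 SD (one-sided 0.025). For a margin of 0.5 SD the power is 56%, and 80% would need 34 patients. For 0.3 SD it is 25%, and 80% would need 90 patients.

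**The case against.** The best defence is that this is a phase 1 safety and feasibility study with 48 hours of sustained LFS, and that much of its safety plan is not significance testing. Individual review, halting and committee looks protect patients, and for those elements noise tends to produce more apparent signals. That stands. A reader might infer that safety is examined only by significance tests; sections 14 and 15 show otherwise. But these elements supply no interval or group-level limit, so they do not close the gap.

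Other stronger readings also go beyond the documents:
- A reader might infer that a non-significant test will be taken as proof of safety. No such rule is written. Section 12(a) states a hypothesis, and the reading of a null result is simply left open.
- A reader might call this the primary hypothesis. The protocol puts safety first but does not rank its safety endpoints.
- A reader might say that real harm would usually be missed. That holds at 0.3 SD and 0.4 SD but fails at 0.5 SD, where detection (56%) is more likely than a miss (44%).
- The paired-t power figures describe the UPDRS test and should not be carried over to the BDI and NPI ANOVAs.
- The documents give no clinically important difference, so they cannot show that 0.3 or 0.5 SD is clinically large.

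It is also fair to object that an interval does not cure what the estimate mixes together. The UPDRS change spans surgery as well as LFS, and patients stopped for their BDI score may be missing from the final-session means. Both limits have to be stated with the result.

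**Conclusion.** The point holds as a gap in group-level inference and reporting. The planned tests cannot support the hypothesis of no harm, and the plan contains neither the estimates with intervals nor a limit that could. A null UPDRS result at n = 20 has an interval reaching 0.47 SD either side of the observed mean change, and up to about 0.94 SD on the worse side if the result is just short of significance. Zero BDI conversions would still be compatible with 16.8%. These figures rest on two-sided alpha 0.05 (95% limits) and 20 evaluable patients, with complete pairs for the UPDRS; fewer would widen them.

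The documents do not support calling the plan wrong as written, because they never state the faulty inference. The right label is a cheap improvement: better estimates from data already being collected.

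**What to change.** In the Safety Data Analysis text of sections 14 and 15:

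1. Report the mean change with a 95% confidence interval for UPDRS motor, BDI and NPI, and the BDI conversion percentage with an exact 95% interval.
2. Describe safety by the worse limit of each interval, and state that a non-significant test will not be reported as no effect.
3. If the investigators want a conclusion of no worsening, name beforehand the change that the limit must exclude. Powering for a tight margin is not reasonable at this stage, and reporting against a stated limit needs no extra patients.
4. State that the UPDRS change runs from before surgery to the final session, so it mixes surgery with LFS.
5. Count patients stopped for their BDI score in the conversion percentage and show their last available scores, since they may be absent from final-session means.
6. Reconcile the definition of conversion before computing it: section 11 counts a BDI score above 20, while sections 14 and 15 count a score of 20 or more.

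The cost is a few sentences and some extra output, with no new patients, visits or measurements. The downside is a more guarded safety statement.
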